3.6.5 Per-protocol Population

The per-protocol (PP) population will include all subjects in the efficacy population who complete the study without any major protocol deviations that would affect the assessment of the efficacy endpoints. In some cases, subjects may be retained in the PP population with partial data up to the point of a major deviation.

If a subject did not treat a bleeding event per the protocol, the PP analysis may exclude the bleeding event in question, rather than all of the subject's data. Accordingly, the following events will be assessed for exclusion from the PP analysis:

- use of a FIX product other than rIX-FP to treat a bleeding event;
- treating a bleeding event ≥ 4 hours after the start of the bleeding event, or
- treating a bleeding event that occurred more than x days and 12 hours after the subject's last prophylaxis dose in the x-day schedule, where x is either 7, 10 or 14

A full review of the bleeding event data will be performed to identify other bleeding events that should be removed from the analysis. Rationale for the reason these bleeding events are being excluded will be provided in the data review meeting minutes before database lock.

No PP population will be used for analysis of PUP data.

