4.10 Compliance

Compliance will be defined in terms of the following:

- the prophylaxis schedule, i.e., “prophylaxis compliance”
- the prescribed dose, i.e., “dose compliance”
- time to on-demand treatment of a bleeding event, i.e., “treatment compliance”

Prophylaxis compliance will be derived as:

$$\frac{\text{(number of on-schedule prophylaxis infusions received)}}{\text{(expected number of prophylaxis infusions)}} * 100$$

where on-schedule prophylaxis infusions are injections during the study period that occur at the expected dosing frequency within the defined target days.

Dosing for each prophylaxis regimen is expected to occur within the following target days:

- For the 7-day regimen, injection of rIX-FP occurs between days 6 and 8 after the previous prophylaxis injection.
- For the 10-day regimen (i.e., every 10 days or 3 times per month), injection of rIX-FP occurs between days 8 and 11 after the previous prophylaxis injection.
- For the 14-day regimen, injection of rIX-FP occurs between days 13 and 15 after the previous prophylaxis injection.
- For the 21-day regimen, injection of rIX-FP occurs between days 20 and 22 after the previous prophylaxis injection.

Dose compliance will be derived as follows:

$$(\text{number of doses within 10\% of the prescribed dose}) / (\text{number of doses received}) * 100$$

Treatment compliance will be derived as follows:

$$\frac{(\text{number of bleeding events treated with rIX-FP } < 4 \text{ hours after the start of a bleeding event})}{(\text{number of bleeding events treated with rIX-FP})} * 100$$

A subject will be defined as compliant with each of prophylaxis regimen, dose, or treatment if the compliance is $\geq 80\%$.

Prophylaxis, dose, and treatment compliance will be summarized by prophylaxis regimen in the safety population using descriptive statistics. Summaries will include the number and percentage of subjects who were compliant with their prophylaxis regimen, dose, treatment, the number and percentage of subjects who were $\geq 80\%$ for each measure, and the number and percentage of subjects who were $< 80\%$ compliant for each measure. Subject listings that include all derived compliance measures for each subject will be provided.

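### The per-protocol rule in SAP 3.6.5 lets individual bleeds be dropped from bleeding rates for late treatment or late timing in the dosing interval, with no rule for the matching time at risk

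*SAP*

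**What the plan says.** SAP 3.6.5 defines the per-protocol (PP) population and then adds an event-level rule. If a bleed was not treated per protocol, "the PP analysis may exclude the bleeding event in question", while the rest of that subject's data stay in. It says that "the following events will be assessed for exclusion from the PP analysis", and lists three grounds:

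- "use of a FIX product other than rIX-FP to treat a bleeding event";
- treatment 4 hours or more after the bleed began;
- "treating a bleeding event that occurred more than x days and 12 hours after the subject's last prophylaxis dose in the x-day schedule", with x being 7, 10 or 14.

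A data review may identify further bleeds to remove, with reasons minuted before database lock. The PP population is not used for previously untreated patients (PUPs).

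SAP 4.12.3 defines ABR as bleeds divided by observed days, times 365.25. Only bleeds requiring rIX-FP count. A subject with no treated bleeds on a regimen has a missing ABR. The days come from SAP Table 2, which ends a regimen period x days after the last rIX-FP infusion unless another stop comes first.

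SAP 4.10 sets the dosing windows that count as on schedule: "For the 14-day regimen, injection of rIX-FP occurs between days 13 and 15 after the previous prophylaxis injection". The other windows are Days 6 to 8, 8 to 11 and 20 to 22 for the 7-, 10- and 21-day regimens. Protocol 6.3 gives the same windows.

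**The concern.** ABR on prophylaxis measures whether the regimen prevented bleeding. How quickly a bleed was treated is settled after it has occurred. A bleed treated at five hours still happened on assigned prophylaxis, during time that counts in full. Dropping it conditions the outcome on something that follows the outcome.

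The timing ground has a better rationale, since a bleed during overdue dosing is arguably not a failure of the regimen. But the cut is set earlier than the SAP's own limit for on-schedule dosing, and the text does not say what happens to the overdue time. It also leaves out the 21-day regimen, which appears in Table 2 and in the descriptive row of Table 3.

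At stake is whether a PP bleeding rate, if produced, can support the efficacy-population result. A rate whose events were filtered in this way is a weak check.

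**Working it through.** The documents give no PP rate or power figure that depends on this rule, so there is no plan figure to reproduce. The checks below use the SAP 4.12.3 formula, ABR = bleeds / days × 365.25.

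**One subject, denominator fixed.** Take 3 bleeds in 730.5 days.
- All bleeds: 3 / 730.5 × 365.25 = 1.50.
- One deleted, time kept: 2 / 730.5 × 365.25 = 1.00.
- One deleted with a 7-day gap: 2 / 723.5 × 365.25 = 1.01.
- One deleted with a 14-day gap: 2 / 716.5 × 365.25 = 1.02.
- Days that would have to go to return to 1.50: 730.5 × 1/3 = 243.5.

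Removing only the gap that held a bleed therefore hardly changes the rate. Overdue time has to be removed wherever it occurs, whether or not a bleed fell in it.

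**Size.** Deleting a share p of bleeds over fixed time multiplies the rate by (1 − p). SAP 4.10 calls a subject treatment-compliant when at least 80% of treated bleeds are treated in under 4 hours. In such a subject, up to 20% of bleeds could meet the late-treatment ground. With the total ABR of 4.4 per year from the phase 1/2 prophylaxis group (Protocol 1.2.3.2, n = 13), 4.4 × 0.8 = 3.5. For p from 5% to 30% the result runs from 4.4 × 0.95 = 4.2 to 4.4 × 0.70 = 3.1. The documents give no frequency of late treatment.

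**Summarised mean.** Four subjects with 1, 4, 8 and 12 bleeds over 2 years each have ABRs of 0.5, 2, 4 and 6, mean 3.125. Delete the first subject's only bleed:
- kept at zero: (0 + 2 + 4 + 6) / 4 = 3.00;
- missing under SAP 4.12.3: (2 + 4 + 6) / 3 = 4.00.

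The crude rate moves from 25/8 = 3.125 to 24/8 = 3.00, or to 24/6 = 4.00 if his time also leaves.

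**Simulation (illustrative).** Assumptions: gamma-Poisson counts, 20 subjects, 1 or 2 years each, 5% to 30% of bleeds deleted at random, rates and SDs from the phase 1/2 group (spontaneous 1.3, SD 1.5; total 4.4, SD 4.7), 20,000 runs.

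| Scenario (1 year, 10% deleted) | Mean before | Mean after | Runs with a rise |
|---|---|---|---|
| Spontaneous, zeros kept | 1.30 | 1.17 | 0% |
| Spontaneous, zeros missing | 2.09 | 1.98 | about 16% |
| Total, zeros missing | 5.32 | 4.88 | about 4% |

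Under the missing rule, the mean fell on average in every scenario and rose in 0% to 16% of runs.

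**Between-regimen difference (7-day minus 14-day).** Start from 2 − 3 = −1. Deleting one bleed per year on the 14-day regimen gives 2 − 2 = 0. Deleting one on the 7-day regimen gives 1 − 3 = −2. The shift can go either way.

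**Timing cut against the dosing windows.**

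| Regimen | Cut | On-schedule limit | Compliant stretch where a bleed qualifies |
|---|---|---|---|
| 7-day | Day 7.5 | Day 8 | 12 hours |
| 10-day | Day 10.5 | Day 11 | 12 hours |
| 14-day | Day 14.5 | Day 15 | 12 hours |
| 21-day | none | Day 22 | no cut |

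Two protocol provisions produce the same clash. Protocol Table 1 allows the 10-day regimen to be given on the 1st, 11th and 21st. In a 31-day month the last gap is 11 days, so its final 12 hours qualify although dosing is on schedule. Protocol 3.2.2 lets prophylaxis be delayed after on-demand treatment, up to one interval from the last bleed treatment. Suppose a 14-day subject is treated for a bleed on Day 10 and bleeds again on Day 15. The second bleed is past Day 14.5 from the last prophylaxis dose and qualifies. Table 2 counts from the last infusion of any kind, so time runs to Day 24 and appears to stay in.

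**The case against.** Much of the case against has force.

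- **Direction.** A reader might infer that the rule can only lower the bleeding rate. That holds for one subject's rate, or a crude rate over fixed time. It fails for the summarised mean, because a subject whose only bleed is deleted becomes missing.
- **Benefit to longer intervals.** A reader might infer a bias in favour of the extended regimens. Deletions on the 7-day side count against non-inferiority, and leaving out x = 21 spares 21-day bleeds from the timing ground.
- **Time at risk.** A reader might infer that the SAP says time is kept. It is silent. If the Table 2 stop and the SAP 4.12.3 exclusion of untreated periods apply to each dosing gap, some overdue time may already be out. This does not help the late-treatment ground, where the time is ordinary on-regimen time.
- **Other product.** Only bleeds requiring rIX-FP enter any ABR. This ground therefore matters only for bleeds that also received rIX-FP.
- **Discretion.** Exclusions are assessed, not automatic, and reasons are minuted before lock. In an open-label study this limits the problem but does not remove it.
- **Purpose.** The PP population serves the efficacy endpoints generally. Treatment timing and product can matter for hemostatic response. Part of the SAP's efficacy section is redacted, so PP use cannot be assumed to be confined to ABR.
- **Reach.** Protocol 11.3.2 makes PP analyses optional, Table 3 has no PP row, PUPs are excluded, and SAP 3.1 says the PTPs were already reported in March 2019. All of this stands. Even so, the current SAP states that it contains all PTP analyses, and Protocol 14.7 has the PTP report integrated into the final report.

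**Conclusion.** The concern holds in a limited form. For any PP analysis of PTP bleeding rates, SAP 3.6.5 permits bleeds to be dropped on a ground unrelated to whether prophylaxis prevented them, and on a timing ground that conflicts with the SAP's own compliant windows and skips one regimen. No rule matches the time at risk. Subject-level and fixed-time crude rates cannot rise and will usually fall. The mean may move either way, and between-regimen contrasts are indeterminate.

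The figure of 4.4 to 3.5 per year is an upper-bound illustration. It assumes a subject exactly on the 80% threshold, every late-treated bleed deleted, and a rate borrowed from 13 subjects on weekly prophylaxis. It is not an estimate for this trial.

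A reader might go further and infer that the non-inferiority conclusions are compromised. The documents do not support that: the fixed sequence in SAP 4.12.3 rests on the Table 3 populations, none of which is PP. The point is minor.

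**What to change.** In SAP 3.6.5, for PP annualized spontaneous and total bleeding rates:

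1. Do not exclude bleeds because of time to treatment or product used. Those grounds may stay for hemostatic-response endpoints.
2. For overdue prophylaxis, remove bleeds and time together from the end of the compliance window (Day 8, 11, 15 or 22) to the next dose, for all four regimens. Apply this from the dosing record to every overdue stretch, whether or not a bleed fell in it. State how delays permitted by Protocol 3.2.2 are counted.
3. Where PP rates have already been reported for PTPs, show them with and without event-level exclusions.

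The cost is a wording change, a small derivation change, a supplementary table if PP rates were reported, and slightly less favourable PP rates.

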3.6.6 Pharmacokinetic Population

The PK population will include subjects who have received at least 1 dose of rIX-FP for the purpose of PK sampling and have a sufficient number of analyzable PK blood samples (i.e. at least 1 PK parameter calculated) for PK assessment of rIX-FP. Subjects will be excluded from the analysis if an insufficient number of analyzable PK samples were obtained to permit the evaluation of at least 1 PK parameter for rIX-FP, excluding samples obtained after receiving a dose of rIX-FP or any other FIX product for the treatment of a bleeding event during the PK sampling period.

3.6.7 Surgical Population

The surgical population, which is a subset of the safety population, will include all PTPs who have provided written informed consent for the surgery substudy and received at least 1 dose of rIX-FP for any surgical procedure in this substudy.

3.6.8 Subcutaneous Safety Population

The subcutaneous safety population, which is a subset of the safety population, will include all PTPs who have provided written informed consent for the SC substudy and received at least 1 SC dose of rIX-FP in the SC substudy.

3.6.9 Subcutaneous PK Population

The subcutaneous PK population will include all PTPs who received at least 1 SC dose of rIX-FP and have blood samples drawn for PK assessment. Subjects will be excluded from analysis if an insufficient number of analyzable PK samples were obtained to permit the evaluation of at least 1 PK parameter for rIX-FP, excluding samples obtained after receiving an IV dose of rIX-FP or any other FIX product for the treatment of a bleeding event during the PK sampling period.

3.7 Randomization

This is a non-randomized study.

3.8 Blinding

This is an open-label study.

4 Statistical Analyses and Methods

4.1 General Considerations

Data management and statistical analyses will be performed by a contract research organization (CRO) under the supervision of CSL Behring. Data manipulations and statistical analyses will be performed using SAS® version 9.2 ([SAS Institute](#)) or higher.

Continuous variables will be summarized in terms of the mean, standard deviation (SD), median, minimum and maximum. Other descriptive statistics (e.g., quartiles, coefficient of variation) may be reported when appropriate. Categorical variables will be summarized using frequency counts and percentages. In general, data will be summarized by treatment arm, regimen, regimen within treatment arm (as applicable), age group, and will include the total subjects in the population. Unless otherwise noted, the denominator for the percentages will include all subjects in the respective treatment arm or regimen. Tables, listings and figures will be presented separately for PTPs and PUPs unless otherwise noted. Analyses of data for PUPs will be descriptive unless otherwise stated.

Unless otherwise specified, all confidence intervals (CIs) and p-values will be two-sided.

For summary tables of PTP data by regimen, the 10-day regimen will be combined with the 3x-per-month regimen. The only exception will be for disposition where separate counts and percentages will be displayed for these regimen groups as collected on the eCRF.

Supportive listings for summary tables and figures will be provided as applicable.

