4.1.5 Early Withdrawal or Missing data

Apart from the handling of partial dates, and derivation of annualized bleeding rates, no imputation due to withdrawals or missing data will be applied for analyses of efficacy or safety endpoints.

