4.5 Protocol Deviations

The number and percentage of subjects who had major protocol deviations will be summarized for the safety populations.

Major protocol deviations will be summarized by categories of deviation. All protocol deviations that have been documented throughout the study will be presented in subject listings for all subjects. Separate listings will be provided for PTP subjects in the efficacy population who were excluded from the PP population.

The summary of major protocol deviations for PUPs will also include deviations associated with COVID-19, and the source listing will flag these deviations.

Planned visits that were missed due to COVID-19 will be summarized for PUPs. A by-subject listing of missed visits due to COVID-19 will be included.

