4.13.2 Inhibitors to Factor IX

The development of inhibitors against FIX is defined as any inhibitor identified at a concentration of ≥ 0.6 BU/mL and confirmed with retesting to be ≥ 0.6 BU/mL. Both tests must be performed by a central laboratory. The incidence of inhibitor development and 95% CI will be presented separately for PTPs and PUPs in the safety population.

For estimating the incidence of inhibitors against FIX in PTPs, the numerator will include all PTPs with inhibitors regardless of EDs to rIX-FP; the denominator will include PTPs with at least 100 EDs plus PTPs with less than 100 EDs who have confirmed inhibitors as follows:

Incidence of inhibitors against FIX in PTPs = number of PTPs who develop inhibitors up to 100 EDs (i.e. ≤ 100 EDs) / (total number of PTPs with at least 100 EDs (≥ 100 EDs) + PTPs with < 100 EDs who have confirmed inhibitors)

PTPs not tested at ≤ 100 EDs will be excluded.

For estimating the incidence inhibitors against FIX in PUPs, the numerator will include all PUPs with inhibitors to rIX-FP; the denominator will include PUPs with at least 50 EDs plus PUPs with less than 50 EDs but with confirmed inhibitors as follows:

Incidence of inhibitors against FIX in PUPs = number of PUPs who develop inhibitors / (PUPs with ≥ 50 EDs + PUPs with < 50 EDs who have confirmed inhibitors).

PUPs not tested at ≤ 50 EDs will be excluded.

The number of subjects with antibodies to plasma-derived factor IX (pdFIX), recombinant FIX (rFIX), albumin, and CHO cells will be tabulated by age group and total.

The two-sided Wald and Clopper-Pearson 95% CI ([Clopper C](#), [Pearson ES](#)) for the incidence of FIX inhibitor formation will be provided. Example SAS code for this procedure is provided below:

```
proc freq data=data order=freq;
  tables inhibitor / binomial(exact);
  weight pos;
run;
```

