Related AEs are AEs considered by the investigator to be related to study treatment.

TEAEs leading to withdrawal from study or withdrawal from study medication are any TEAEs reported on the AE log with "Was subject terminated from study due to the AE" as "Yes" or "Action taken with study drug" with response of "Permanently discontinued" respectively.

Adverse events of special interest (AESI) will include preferred terms associated with the following Standard MedDRA Queries (SMQs) based on narrow search criteria:

1. Anaphylactic reactions
2. Embolic and thrombotic reactions
3. Hypersensitivity

AEs will be reported separately for the surgery substudy, subcutaneous substudy, main study (prophylaxis and PK period), and overall (all periods). The following will be summarized by SOC and PT for the number and percentage of subjects who experience at least 1 event and the total number of events:

- all AEs including AESIs
- all SAEs
- TEAEs, overall and by regimen
- related TEAEs
- TEAEs occurring \leq 72h after infusion of study medication
- non-serious TEAEs
- SAEs
- related treatment-emergent SAEs
- TEAEs by maximum severity (If a subject experiences multiple events that map to a single PT, only the most severe event will be counted.)
- TEAEs by highest relationship and maximum severity (If a subject experiences multiple events that map to a single PT, only the related event and the most severe will be counted.)
- TEAEs leading to withdrawal of study medication
- TEAEs leading to death
- TEAEs by every six-month time intervals (not applicable for PUPs)

SOCs will be displayed by decreasing frequency, and PTs will be displayed in decreasing frequency by subject.

TEAEs also will be presented for the following subgroups:

- subjects \geq 18 years who switched from 14-day regimen to 21-day regimen
- subjects \geq 18 years who switched to 21-day regimen compared with subjects \geq 12 years not switching
- subjects $<$ 12 years in 14-day regimen
 - paired subjects who had 7-day and 14-day regimen in CSL654_3003
 - subjects in CSL654_3003 14-day regimen
 - subjects in CSL654_3002 who had 14-day regimen in CSL654_3003

- subjects <12 years who switched to 14-day regimen compared with subjects <12 years not switching

TEAEs will be counted in the respective regimen based on the onset time of the TEAE.

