4.13.5 Laboratory Safety Parameters

Laboratory results along with the change from baseline will be summarized by parameter and study visit. The change from baseline to the lowest value after first dose of study product, highest value after first dose of study product, and final value will also be summarized. For laboratory parameters with positive or negative results, the number and proportion with positive treatment-emergent results will be summarized at each visit.

Laboratory values will be converted to the standard units of measurement for summary displays.

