4.13.6 Antibodies to rIX-FP and CHO Cell-derived Proteins

The number and percentage of subjects with rIX-FP and CHO cell-derived protein antibody titers above the cut-off level for the respective confirmation assays will be tabulated.

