- The minimum and maximum values will be presented with the same number of decimal places as the raw data collected. The mean and percentiles (e.g. median, Q1, and Q3) will be presented using 1 additional decimal place. The SD and standard error will be presented using two additional decimal places. PK parameters should have a minimum of 3 significant figures.
- Percentages will be presented to 1 significant decimal place in general. The denominator will be the total size of the sample, N, unless otherwise noted.
- Percentages greater than 0 but less than 1% will be reported as <1%, whereas percentages greater than 99% but less than 100% will be reported as >99%. A percentage of 100% will be reported as 100%. No value of 0% will be reported. A computation of a percent that results in 0% will be left as blank, i.e., a numerator of 0 will be reported, however no percentage will be reported. This principle applies to portions of a whole and does not apply to differences or changes measured as percentages. Increased precision may be warranted on occasion.
- Any p-values reported on default output from statistical software may be reported at the default level of precision, with 1 exception: p-values of 0.0000 or 10E-4 or below will be reported as <0.0001.

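### The SAP's all-subjects denominator has no stated exception for antibody, by-visit positive-result or six-month TEAE percentages, so untested or withdrawn subjects would count as event-free

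*SAP*

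**What the plan says.** The default appears twice. SAP 4.1: "Unless otherwise noted, the denominator for the percentages will include all subjects in the respective treatment arm or regimen". SAP 9.1: "The denominator will be the total size of the sample, N, unless otherwise noted".

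Three safety displays give a percentage or proportion without naming another denominator:

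- SAP 4.13.3 lists "TEAEs by every six-month time intervals (not applicable for PUPs"), among tables reporting the number and percentage of subjects with an event.
- SAP 4.13.5, for laboratory parameters with positive or negative results: "the number and proportion with positive treatment-emergent results will be summarized at each visit".
- SAP 4.13.6: "The number and percentage of subjects with rIX-FP and CHO cell-derived protein antibody titers above the cut-off level", where each confirmation assay has its own cut-off.

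FIX inhibitor incidence is treated differently. SAP 4.13.2 builds a denominator from exposure days and adds "PUPs not tested at ≤ 50 EDs will be excluded", with a matching rule for PTPs at 100 exposure days.

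On missing data, SAP 4.1.5 says that, apart from partial dates and bleeding-rate derivation, "no imputation due to withdrawals or missing data will be applied for analyses of efficacy or safety endpoints". Protocol 11.3 limits summaries to available data unless the SAP specifies otherwise, and the SAP's opening section gives the SAP precedence over the protocol.

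**The concern.** A percentage on all N treats everyone without an observation as a non-event. A subject with no post-dose antibody sample would count as antibody-negative. A subject with no sample at a visit would count as negative at that visit. A subject who left before a six-month interval would count as free of adverse events in it. This amounts to imputing a favourable value, which SAP 4.1.5 says will not be done.

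The design allows such gaps. Follow-up in Arms 1 to 3 differs between subjects (SAP 3.2: about 5 years or the time to 100 exposure days, with site closure possible on commercial availability). Arm 4 subjects who are dosed infrequently may omit early visits (note I to Table D in the protocol). For Arm 4 the SAP also provides that "Planned visits that were missed due to COVID-19 will be summarized for PUPs".

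At stake is the readability of descriptive safety tables: too low a percentage where subjects are untested and, in a table by interval, a decline over time produced by attrition alone.

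**Working it through.** The documents state no figure for these percentages and no withdrawal, testing or event rates. There is nothing to reproduce, and every rate below is an assumption.

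**Formula.** With x subjects with the event among m observed, and N in the arm or regimen:

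- on all N: x/N = (x/m) × (m/N)
- on those observed: x/m

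The all-N percentage is therefore the observed risk multiplied by m/N. The two agree when m = N.

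**Inputs for N.** At least 13 PUPs (SAP 3.3) and 83 PTPs (protocol revision history, Amendment 6). These agree with the planned total: 83 + 13 = 96.

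**PUP display, one positive result.** On all N it is always 1/13 = 7.7% (exact 95% CI 0.2 to 36.0). The number tested is assumed.

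| Tested | On those tested |
|---|---|
| 13 | 1/13 = 7.7% |
| 12 | 1/12 = 8.3% |
| 10 | 1/10 = 10.0% |
| 9 | 1/9 = 11.1% |
| 8 | 1/8 = 12.5% (CI 0.3 to 52.7) |
| 6 | 1/6 = 16.7% (CI 0.4 to 64.1) |

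**PTP six-month table, N = 83.** Assume a constant risk of about 30% per interval among those still in the study, rounded to whole subjects.

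| Already left | At risk | With event | On 83 | On at risk |
|---|---|---|---|---|
| 0% | 83 | 25 | 30.1% | 30.1% |
| 10% | 75 | 22 | 26.5% | 29.3% |
| 25% | 62 | 19 | 22.9% | 30.6% |
| 50% | 42 | 13 | 15.7% | 31.0% |
| 75% | 21 | 6 | 7.2% | 28.6% |

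The same effect over time: with a constant 40% risk and 3%, 5% or 8% leaving per interval, the tenth interval (5 years ÷ 6 months = 10) would show 0.40 × 0.97⁹ = 30.4%, 0.40 × 0.95⁹ = 25.2% or 0.40 × 0.92⁹ = 18.9%.

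**Which tables are still to be produced.** SAP 4.13.3 marks the six-month table as not for PUPs. SAP 3.1 says that PTPs were analysed in a clinical study report dated 14 March 2019 and will not be analysed again. SAP 3.4 says that this version focuses on Arm 4. The tables still to come are therefore the PUP antibody percentages and any PUP positive/negative display by visit.

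**The case against.** The case on the other side is strong on scope.

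- **The six-month trend is not forthcoming.** A reader might infer that the coming analysis will show a false fall in adverse events. The documents do not support that, because the table is PTP-only and already reported. The missed-visit provision for COVID-19 covers PUPs only, so it is no evidence of missingness in that table. This stands.
- **No parameter is named for the by-visit table.** SAP 4.13 describes laboratory safety parameters as serum chemistry and hematology, and nothing in the protocol's panel (Table 2) is a positive/negative test. The 4.13.5 sentence has effect only if it is also applied to inhibitor or antibody results. This stands, and it makes the by-visit effect conditional.
- **The antibody percentage is robust to a single missed visit.** Section 4.13.6 reads as one tabulation per subject. Arm 4 antibody samples are due at Months 6, 12 and 24, at 50 exposure days and at end of study, and Protocol 4.2.2 asks sites to attempt end-of-study assessments after withdrawal. Only a subject with no post-dose sample at all is miscounted. This stands.
- **Counts accompany the percentages, and no formal comparison is planned.** With about 13 PUPs the count carries most of the information, and the intervals above are far wider than the shift. This limits the importance but does not make the percentage right.
- **The table shells may note other denominators.** They are a separate document (SAP 9.2) and were not available. They might resolve the point, but a programmer working from the SAP text would use N. The no-imputation and available-data statements do not override an explicit denominator rule; they show that the intention is unclear.

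**Conclusion.** The gap is real and its reach is limited. The SAP states an all-subjects denominator twice, makes an exception for FIX inhibitor incidence, and makes none for the three displays. Followed literally, those percentages shrink by observed/N, contrary to SAP 4.1.5.

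It would be tempting to conclude that every late safety percentage in the study is biased downward. The documents do not support that: the primary inhibitor incidence excludes untested subjects, the denominators agree when nobody is missing, and no missingness rate is given. The size is therefore unknown. For PUPs, one positive in 13 reads 7.7% against 8.3% to 16.7% if 12 to 6 were tested, including 11.1% at 9. These are illustrations over an assumed range.

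The observed-subject percentage also describes only those observed. It represents the whole arm only if missing subjects would have had the same risk, which neither denominator can show.

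**What to change.** Add three exceptions to SAP 4.1, with a cross-reference in 9.1:

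1. Percentages by visit use subjects with a non-missing result at that visit.
2. Antibody percentages use subjects with at least one post-dose result.
3. Six-month TEAE percentages use subjects under observation at the start of the interval.

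Show that n in each table beside N. State in 4.13.5 which positive/negative parameters, if any, the by-visit table covers. For the PTP six-month table, check which denominator the 2019 report used and show n at risk there; no re-analysis in the PUP report is implied.

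The cost is a few sentences, a denominator change in the table programs and a check of the shells. No new data are needed. The downside is that some percentages become slightly less favourable and rest on smaller, less stable denominators.
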